- Change from baseline in overall clinical SD score at 4 weeks of treatment with ruxolitinib 1.5% cream applied twice daily

- Change from baseline in each component of the clinical SD score at 4 weeks of treatment with ruxolitinib 1.5% cream applied twice daily (scale, erythema, pruritus)
- Change in overall clinical SD at 6 weeks (i.e., 2 weeks after treatment cessation) from baseline and from 4 weeks
- The frequency, duration, and severity of AEs
- Changes in vital signs
- Changes in laboratory data for hematology, serum chemistry, and urinalysis

Mechanistic (Exploratory) Endpoints

- Determine the molecular cutaneous phenotype of SD at baseline compared with healthy controls, using transcriptomic and proteomic approaches from skin samples acquired by tape-strips
- Identify molecular markers that correlate with disease activity in SD at baseline
- Characterize the change in molecular responses with treatment of topical ruxolitinib 1.5% cream after 4 weeks of treatment
- Identify molecular markers that correlate with treatment response at 4 weeks

STUDY DESIGN OVERVIEW:

This study is an open-label prospective interventional trial. The study will take place at Icahn School of Medicine at Mount Sinai.

The study will include 25 adult patients with moderate-to-severe-SD as well as 20 age- and gender-matched healthy control subjects for comparison. The SD patients will have baseline clinical score of at least 6 using the SD Severity Score in Appendix 1, or an Investigator Global Assessment (IGA) score of at least 3. Enrolled SD subjects will apply topical ruxolitinib 1.5% cream twice daily for 4 weeks. They will return for visits at weeks 2, 4, and 6 following study treatment initiation for repeat clinical assessments, medication reviews, tape-strip, blood and urine sample collections, and monitoring for adverse events.

After providing consent, all subjects will be assessed for study eligibility, which includes a review of the subjects past and current medical conditions, familial medical history and detailed review of past and current medications. SD subjects will also undergo a review of past topical treatments/therapies for SD, and clinical assessments (clinical SD score and IGA).

Subjects who meet inclusion criteria for eligibility may continue with the Baseline Visit (Week 0) or can be scheduled to return for the Baseline Visit within 28 days of the Screening Visit.

SD Subjects:

Seborrheic Dermatitis Ruxolitinib Cream Protocol
Incyte IIR

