The reasons why a subject may discontinue or be withdrawn from the study by the investigator include, but are not limited to the following: subject request, protocol violation, loss to follow up, subject non-compliance, defined as 4 missed applications during the 2 week period between study Visits, study termination by investigators, and a confirmed grade 3 or higher adverse event, which is suspected to be related to study drug administration. Subjects that elect to withdraw from the trial due to lack of efficacy and/or exacerbation of disease will undergo the following: vital signs; blood test; pregnancy test (if applicable); clinical photography; SD clinical assessments; DLQI questionnaire, assessment of concomitant medication and adverse events; blood collection for future mechanistic analysis; lesional tape strip collection.

Stopping Rules

Patients will be permanently discontinued from study treatment in the event of:

- Anaphylactic reaction or other severe systemic reaction to study drug application
- Pregnancy at anytime during the study period
- Diagnosis of a malignancy during study, excluding carcinoma in situ of the cervix, or squamous or basal cell carcinoma of the skin
- Any infection that is opportunistic, whose nature or course may suggest an immuno-compromised status
- Treatment with any prohibited concomitant medication or procedure
- Other reasons that may lead to the permanent discontinuation of study drug include certain Aes deemed related to the study drug.
- If the following lab results are abnormal, participants will be retested in a window of 7-10 days and reassessed. If the test results remain abnormal, participants will be discontinued from the study:

Hematology

Absolute Neutrophil Count: $<1000/\text{mm}^3$; $<1.0 \times 10^9/\text{L}$

Hemoglobin: $<8.0 \text{ g/dL}$; $<4.96 \text{ mmol/L}$; $<80 \text{ g/L}$

Hemoglobin drop $\geq 2 \text{ g/dL}$ from baseline on two consecutive blood draws with associated symptoms; or hemoglobin drop $\geq 3 \text{ g/dL}$ from baseline on two consecutive blood draws without associated symptoms.

Platelet count: $<75,000/\text{mm}^3$; $<75.0 \times 10^9/\text{L}$

Lymphocytes: $<500/\text{mm}^3$; $<0.5 \times 10^9/\text{L}$

Chemistry

AST $>3.0 \times \text{ULN}$

ALT $>3.0 \times \text{ULN}$

Total bilirubin $>1.5 \times \text{ULN}$

CPK $>10 \times \text{ULN}$

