An "Initial Pregnancy Report" or equivalent must be completed in full and emailed to [contact] or faxed to [name] within 24 hours of discovery of a pregnancy of a subject who has taken the Incyte product or the pregnancy of a partner for a subject who has taken the Incyte product. The "Follow-up Pregnancy Report Form" or equivalent must be completed and emailed to [contact] or faxed to [name] within 30 days after delivery, so that Incyte is provided with information regarding the outcome of the pregnancy. If the pregnancy results in any events which meet the serious criteria (i.e., miscarriage or termination), the SAE reporting process needs to be followed and the timelines associated with a SAE should be followed.

SUBJECT IDENTIFICATION

Subjects are numbered sequentially. Each subject will be assigned a unique screening number for the duration of the study. Subject screening numbers will not be reassigned or reused for any reason. The investigator must maintain a master log linking the subject number to the subject's name. The investigator must follow all applicable privacy laws in order to protect a subject's privacy and confidentiality.

STUDY DRUG SUPPLY:

Seborrheic Dermatitis Ruxolitinib Cream Protocol
Incyte IIR
March 25, 2022

Eligible patients will receive a supply of ruxolitinib 1.5% cream which they will apply to affected skin on the face only twice daily. Patients will be instructed not to use more than 60g of cream per week.

All study medication will be stored in a secure cool area between 15-30°C. Study drug will be provided to subjects at each study visit, with initial application performed at that time and subsequent applications performed by the patients at home.

Subjects will be queried during each study visit on any missed applications.

STATISTICAL CONSIDERATIONS:

Sample Size Calculation

A sample size of n=20 SD patients guarantees 90% power at 2.1% significance to detect a minimum proportion of 75% of patients with IGA 0/1 at week 4. This calculation assumes the application of the one-sided binomial test with a null hypothesis proportion of 40%. This proportion is based on the vehicle response benchmark reported by Zirwas et al.(2021) when comparing IGA 0/1 at week 8 in 154 patients treated with roflumilast foam 0.3% vs. 72 patients in the vehicle-controlled group(18). Accounting for a 20% dropout rate, we, therefore, propose a sample size of n=25 patients.

Mechanistic Endpoint

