To the best of our knowledge, this is the first study to evaluate differences in the transcriptome between SD and healthy subjects. A previous study (19) evaluated a fold-change (FCH) of 5 in IL-10 cell counts with coefficient of variation of 50% when comparing 10 SD subjects to 4 healthy volunteers. Assuming similar variability, a sample size of n = 20 SD subjects and n= 20 controls would provide 90% power at 5% significance to detect FCH>2.65 when comparing IL-10 expression between SD and controls, based on a two-sided unpaired t-test applied to log2-transformed RNA-seq data and fold-changes back transformed.

Demographics and Other Baseline Characteristics

Descriptive statistics of demographics and other baseline characteristics of patients will be summarized. Other baseline characteristics include height, weight, vital signs, duration of SD disease, concurrent diagnoses from medical history and indications for concomitant medication, concomitant medication, and previous SD treatments.

Analysis of Primary Endpoint

The one-sided binomial test will be used to verify the hypothesis that the proportion of patients achieving IGA 0/1 at 4 weeks of treatment with ruxolitinib 1.5% cream applied twice daily is greater than 0.4.

Analysis of Secondary Endpoints

The two-sided Wilcoxon signed-rank test will assess the significance of changes from baseline in:

- IGA score at 4 weeks of treatment
- Components of clinical SD scoring (scale, erythema, and pruritus) at 4 weeks of treatment.

The two-sided paired t-test will assess the significance of changes from baseline in:

- Overall clinical SD scoring at 4 and 6 weeks of treatment.
- Vital signs measured in interval or ratio scale
- Analytes measured in interval or ratio scale from laboratory tests (hematology, serum, chemistry, and urinalysis) at 4 weeks of treatment

The p-values will be adjusted by the Bonferroni method. The frequency, duration, and severity of AEs will be summarized with tables and summary statistics.

Analysis of Mechanistic (Exploratory) Endpoints

The baseline immune and molecular cutaneous profile of SD at baseline compared with healthy controls and the change in the immune and molecular cutaneous profile of SD with treatment will be assessed by MMRM approach. Gene/Protein expression data will be modeled using a mixed effect model with the interaction between tissue type (non-lesional/ lesional / healthy) and timepoint as fixed effects and a random effect for each subject.

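### Laboratory and vital-sign changes are analysed only by a Bonferroni-adjusted test of the mean, and no planned analysis counts patients beyond the protocol's laboratory limits

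*Combined protocol and SAP*

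**What the plan says.** The Secondary Endpoints include changes in vital signs and "Changes in laboratory data for hematology, serum chemistry, and urinalysis". The matching analysis, under Analysis of Secondary Endpoints, begins "The two-sided paired t-test will assess the significance of changes from baseline in" and then lists "Vital signs measured in interval or ratio scale" and "Analytes measured in interval or ratio scale from laboratory tests (hematology, serum, chemistry, and urinalysis) at 4 weeks of treatment". It adds that "The p-values will be adjusted by the Bonferroni method". The plan gives no confidence interval, margin, shift table or count of abnormal values for these endpoints. It also states no significance level for them and does not define the Bonferroni family.

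The protocol treats laboratory harm patient by patient elsewhere. Stopping Rules lists limits for neutrophils, hemoglobin (a level and a fall from baseline), platelets, lymphocytes, AST, ALT, bilirubin and CPK, with the rule "If the following lab results are abnormal, participants will be retested in a window of 7-10 days and reassessed". Persistent abnormality leads to discontinuation. Under Safety Monitoring, an investigator reviews every laboratory result and assesses for AEs. Analysis of Safety and Tolerability provides AE tables by severity and listings by subject. It names no table of laboratory values or vital signs.

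**The concern.** The protocol's laboratory question concerns individuals: did this patient cross a limit? The planned statistic answers a different one: is the average change different from zero? The two can diverge. A few large falls hardly move the mean, and they also inflate the SD in the test's denominator.

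The direction of error matters too. For efficacy, a low chance of rejecting is conservative. For safety, it makes the reassuring result the likely one, and Bonferroni adjustment makes it more likely still. At stake is what the report can say about laboratory safety. Under the plan as written, the prespecified laboratory output is a set of adjusted p-values that are likely to be non-significant in 20 to 25 patients whether or not a moderate effect exists.

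**Working it through.** **Sample size.** The sample size was set by the primary endpoint: "A sample size of n=20 SD patients guarantees 90% power at 2.1% significance to detect a minimum proportion of 75% of patients with IGA 0/1", against a null of 40%, one-sided. With success at 13 or more of 20, the exact binomial gives P(X ≥ 13 | 0.40) = 0.0210 and P(X ≥ 13 | 0.75) = 0.898. Allowing for 20% dropout, 20 / (1 − 0.20) = 25. The stated figures reproduce, so n = 20 (evaluable) to 25 (enrolled) is the relevant range. The documents give no power for the laboratory or vital-sign tests.

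**Assumptions, because the documents give none of these.** Two-sided α = 0.05, a true mean shift of 0.5 SD of the within-patient change, and 20 to 40 tests in the Bonferroni family.

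**Chance of missing the shift.** The paired t-test has df = n − 1 and noncentrality 0.5 × √n, which is 2.236 at n = 20 and 2.500 at n = 25. The miss rate is 1 minus power from the noncentral t.

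| α per test | Missed, n = 20 | Missed, n = 25 |
|---|---|---|
| 0.05 (unadjusted) | 43.5% | 33.0% |
| 0.05/20 | 85% | 78% |
| 0.05/40 | 90% | 84% |

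The shift detectable with 80% power, unadjusted, is 0.66 SD of the change at n = 20 and 0.58 SD at n = 25.

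**Sensitivity to the meaning of SD.** If 0.5 SD refers to the between-patient SD, the standardised shift is 0.5 / √(2(1 − ρ)), where ρ is the correlation between baseline and week 4. The unadjusted miss rates (n = 20 / n = 25) are then 57% / 47% at ρ = 0.3, 44% / 33% at 0.5, 22% / 13% at 0.7 and 8% / 3% at 0.8.

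**A few patients with large falls.** Simulation with 40,000 trials per case: changes are N(0,1) in SD-of-change units, and k patients are shifted by −5. Proportion of trials with unadjusted p < 0.05:

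| Patients shifted | n = 20 | n = 25 |
|---|---|---|
| 1 | 3.4% | 3.6% |
| 2 | 7.3% | 7.8% |
| 3 | 18.1% | 18.0% |

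With one such patient the test rejects less often than the 5% expected with no effect at all. Algebra shows why. If one patient falls by d and the others do not change, the mean is −d/n and the variance is d²(1 − 1/n)/(n − 1) = d²/n. The standard error is therefore d/n and t = −1, however large d is. The 5% critical value is 2.09 at n = 20 and 2.06 at n = 25.

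**What a count would give.** The exact one-sided 95% upper bound for zero events is 1 − 0.05^(1/n): 13.9% for 0/20 and 11.3% for 0/25. For 2/25 the Clopper-Pearson bound is 23.1%.

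**The case against.** A reader might infer that the trial judges safety only by non-significance, or that patients who cross a limit go unseen. The documents support neither reading. No section says that a p-value above a cut-off means safe. Analysis of Safety and Tolerability bases the evaluation on AE tabulations, and Safety Evaluation names AEs, physical examinations and vital signs. Individual crossings are handled by investigator review, by retest and discontinuation, and by AE tables with counts, percentages and listings by subject. That part of the objection stands, and it limits the point to what the statistical plan reports for these endpoints.

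Other parts also stand:

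- The 0.5-SD shift, the 5% level, the number of tests and the 5-SD fall are assumptions. No analyte's SD is given, so nothing shows that a 5-SD fall would cross a limit.
- The protocol gives no vital-sign limits, so the argument about crossings applies to laboratory values only.
- Stopping Rules requires abnormality to persist on retest, and its hemoglobin-fall rule needs two consecutive draws. A count of any single value beyond a limit is therefore not the protocol's criterion and has to be shown separately.
- An upper bound of 11 to 14% from zero events is itself weak reassurance.

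It can also be said that silence does not forbid confidence intervals, and that a paired t-test is built from the mean change and its SD. But the plan states a method, and that method yields adjusted p-values. AE listings fill the gap only when the investigator records the laboratory finding as an AE.

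**Conclusion.** The point holds in limited form. The only statistical analysis planned for the laboratory and vital-sign change endpoints is a Bonferroni-adjusted paired t-test of the mean, and no planned analysis counts patients against the protocol's laboratory limits. Under the stated assumptions the test misses a moderate mean shift in 33.0 to 43.5% of trials unadjusted and in 78 to 90% with adjustment over 20 to 40 tests. The first range depends on reading the SD as that of the within-patient change: with a between-patient SD and a correlation above 0.5 it would be lower. That a single patient's fall, however large, cannot make the test reject by itself depends on neither the 0.5-SD shift nor the number of tests. This is a weakness in the reported safety summary, not evidence that patients are unprotected, and it is cheap to mend.

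**What to change.** In Analysis of Secondary Endpoints, replace the significance testing of laboratory analytes and vital signs with:

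1. For each analyte that is measured and has a limit under Stopping Rules, the number and percentage of treated patients with any post-baseline value beyond the limit and, separately, the number confirmed on retest as that section requires. Give each with an exact one-sided 95% upper bound. The list of limits must be reconciled first: total bilirubin appears twice with different inequality signs, and CPK has a limit but is not named among the collected tests.
2. The mean change with an unadjusted 95% confidence interval for each analyte and vital sign.
3. A statement that any paired t-test is descriptive and outside the Bonferroni adjustment, and that non-significance will not be reported as evidence of no effect.

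Vital signs come under items 2 and 3 only. Their measurement times also need stating, since they appear in neither the visit lists nor the Schedule of Events.

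The laboratory part needs wording and one extra table from draws already scheduled at baseline, Week 4 and Early Termination, plus any retests. It needs no new patients or visits. The downside is a less favourable safety statement, because even zero crossings leaves an upper bound of 11.3% (0/25) or 13.9% (0/20).

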March 25, 2022

At Baseline/Week 0, subjects will undergo clinical assessments (clinical SD Severity Score and IGA), review of concomitant medications, standardized clinical photography, and a Dermatology Life Quality index (DLQI) questionnaire (Appendix 2). Subsequent clinical assessments including standardized clinical photography, and questionnaire completion will be performed at follow up visits at Week 2, Week 4, and Week 6. Skin tape-strip samples will be collected for mechanistic studies (described below) at baseline (lesional and non-lesional facial skin), Week 2 (lesional facial skin), Week 4 (lesional facial skin), and Week 6 (lesional facial skin). Additional blood samples will be collected and stored at baseline and at Week 4 (or early termination, whichever is first) for potential future mechanistic analyses.

Control Subjects:

At Baseline/Week 0, subjects will undergo a review of concomitant medications, skin tape-strip samples will be collected for mechanistic studies (described below) of non-lesional facial skin, blood and urine sample collection for standard laboratory testing, and a blood sample for possible future mechanistic analyses.

MECHANISTIC ANALYSES:

We will characterize the molecular immune profiles of patients with SD at week 0 and week 4, with comparison to baseline profiles in healthy control subjects.

We plan to obtain lesional and non-lesional tape strip samples from facial skin of SD patients at week 0 and lesional facial skin samples at Week 4 (Primary Endpoint). Additionally, lesional facial skin samples will be collected at Week 2 and Week 6 and stored for potential future analysis. Blood samples at baseline and at Week 4 will be collected and stored for potential future analysis.

Gene expression studies on tape strip samples will be performed using Illumina NovaSeq 6000 for RNA-seq, and proteomic studies on tape strip samples will be performed using the Olink Explore panel, which includes >1,500 protein analytes.

PATIENT POPULATION:

Prior to enrollment, all subjects must meet the following inclusion and exclusion criteria:

Inclusion Criteria For SD Subjects:

- 1) Male or female subjects \geq 18 years of age at the time of signing the informed consent document.
- 2) Subject is able to understand and voluntarily sign an informed consent document prior to participation in any study assessments or procedures.

- 3) Subject is able to adhere to the study visit schedule and other protocol requirements.

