- Record all concomitant medications as well as all those received within 30 days prior to screening
- Urine pregnancy test for all female subjects of child-bearing potential
- Record adverse events

* If subject meets all entry criteria at Screening, he/she can complete Baseline Visit on the same day (identical procedures do not need to be repeated). If more than 28 days has lapsed between screening and Baseline/Visit 2, then all procedures should be repeated except for re-obtaining informed consent.

Visit 2 – Baseline (Week 0)

- Confirm all inclusion and exclusion criteria have been met
- Record concomitant medications and adverse events
- Urine pregnancy test for all female subjects of child-bearing potential
- Collect blood samples for CBC with differential, Comprehensive metabolic panel (CMP), and C-reactive protein (CRP)
- Collect blood sample for possible future mechanistic analyses
- Urinalysis
- Perform tape strips of non-lesional skin

SAFETY MONITORING:

The study will be conducted in accordance with our department's Standard Operating Procedures, which are based on US FDA Title 21 Code of Federal Regulations and ICH Good Clinical Practice guidelines. An investigator will review all laboratory results and assess for adverse events. The principal investigator will be informed of all adverse events. In the event that a subject's safety is compromised, the investigator will discontinue the subject immediately.

STUDY WITHDRAWAL:

In the event a study subject wants to withdraw early from the study for any reason, the subject will be asked to return for a final visit to have some or all of the following procedures and assessments as listed for Visit 5/Week 6: vital signs; blood test; pregnancy test (if applicable); clinical photography; SD clinical assessments; DLQI questionnaire, assessment of concomitant medication and adverse events; blood collection for future mechanistic analysis; lesional tape strip collection.

DISCONTINUATION OF TREATMENT AND WITHDRAWAL OF SUBJECTS:

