RNA-sequencing data will be profiled by Illumina NovaSeq 6000. RNA-sequencing data will be pre-processed using standard quality control metrics, such as FastQC and MultiQC, sequence alignment by STAR RNA-sequencing aligner and sequencing reads assignment to genomic features by featureCounts, followed by *voom*-transform. Mixed effect models will be used on R's limma framework and p-values for the moderated t-tests and paired-t-test will be adjusted by Benjamini-Hochberg procedure. Extensive bioinformatics tools will be employed to gain insights into the results. This will include (but will not be limited to) pathway and gene-set enrichment analyses by R package GSVA (Gene Set Variation Analysis) and by eXploring Genomic Relations (XGR) that uses prior biological knowledge and relationships from public databases.

We will perform proteomic biomarker studies in serum using the OLINK high-throughput proteomic platform, with the Explore panel that evaluates >1,500 protein analytes. Protein expression data will be modeled using a MMRM approach, with the interaction of study group (treatment /control) and timepoint as fixed effects and a random effect for each subject.

We will use the Spearman coefficient to correlate: 1) molecular markers with disease activity in SD at baseline; 2) changes from baseline in molecular markers with changes from baseline in IGA and overall clinical SD scoring at 4 weeks of treatment.

Data Transfer and Management

Data including the patient info, demographics, clinical scores and treatment allocation code will be sent to our Biostatistical Team in password-protected files.

Data from the [name] Lab (where all mechanistic studies will be done), including sequencing data and proteomics will be deposited in the Mount Sinai Box, which has the necessary safeguards for protection of human subjects research.

All data management steps taken to reformat and merge the clinical and laboratory data will be carried out using R codes, so all the steps of the processes can be reproduced.

Management of the Analysis

Analyses will be run in our desktops, with a backed-up copy in the Mount Sinai Box account. Once the analysis is finalized, all data will be deposited into the central file storage system (CFS), which is accessible to all research members. Both Mount Sinai Box and the CFS have backup capabilities and are encrypted and password protected.

Analysis of Safety and Tolerability

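### The tissue-by-timepoint and serum group-by-timepoint interactions cannot be estimated, because non-lesional skin, control skin and control blood are collected only at Week 0; the models should be restated as factors over the observed cells with named contrasts

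*Combined protocol and SAP*

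**What the plan says.** Two models are specified in the combined protocol and SAP, under Analysis of Mechanistic (Exploratory) Endpoints.

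- Skin gene and protein expression: a mixed model "with the interaction between tissue type (non-lesional/ lesional / healthy) and timepoint as fixed effects", with a random effect per subject.
- Serum proteins: a repeated-measures mixed model "with the interaction of study group (treatment /control) and timepoint as fixed effects", again with a random effect per subject.

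No main effects, coding, reference level or contrasts are given for either model.

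The sampling is described elsewhere in the same document.

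- **SD skin.** Study Design Overview has tape strips taken "at baseline (lesional and non-lesional facial skin), Week 2 (lesional facial skin), Week 4 (lesional facial skin), and Week 6 (lesional facial skin"). Mechanistic Analyses plans to analyse "lesional and non-lesional tape strip samples from facial skin of SD patients at week 0 and lesional facial skin samples at Week 4"; the others, "lesional facial skin samples will be collected at Week 2 and Week 6 and stored for potential future analysis". The early termination strip is also lesional only (Procedures; Table 1).
- **Control skin.** Controls have a single Screening/Baseline column in Table 1. The only skin instruction at their Baseline visit is "Perform tape strips of non-lesional skin". Mechanistic Analyses describes SD profiles at Weeks 0 and 4 "with comparison to baseline profiles in healthy control subjects".
- **Blood.** For SD subjects, "Blood samples at baseline and at Week 4 will be collected and stored for potential future analysis". Controls give one stored sample, at Baseline.

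The document does not say how the missing tissue-time or group-time combinations are to be handled.

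**The concern.** An interaction with timepoint asks whether one tissue or group changes over time differently from another. That requires both members of the comparison to be measured at both times. Here only lesional SD skin and SD blood are measured after Week 0, so the named terms have no data behind them. The cells are empty by design, and neither more patients nor complete follow-up would fill them.

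Two things are at stake. First, an analyst who enters the models in the usual form will meet a rank-deficient design. Depending on the software, the fit stops or terms are removed, and the meaning of the remaining Week 4 coefficient then depends on a reference level that the plan does not set. Second, a group-by-time term invites a reader to expect a control-adjusted treatment effect on biomarkers, which this design cannot give. The models are to be applied across RNA-seq genes and more than 1,500 proteins, so the reported quantity should be defined beforehand.

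**Working it through.** The plan gives no figure to reproduce. The question is which contrasts the schedule can identify.

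**Inputs.** Observed cells, from Study Design Overview, Mechanistic Analyses, Procedures and Table 1:

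| | Week 0 | Week 4 |
|---|---|---|
| Healthy skin (H) | yes | none |
| Non-lesional SD skin (N) | yes | none |
| Lesional SD skin (L) | yes | yes |
| Control blood (C) | yes | none |
| SD blood (S) | yes | yes |

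**Rule.** A fixed-effect contrast is estimable only if it can be written as a combination of observed cell means. The rank of the fixed-effect design cannot exceed the number of observed cells. Neither depends on n or on the random effect.

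**Skin, Weeks 0 and 4.** Main effects plus interaction need 1 + 2 + 1 + 2 = 6 columns. There are 4 observed cells and the rank is 4. With healthy as reference and columns (intercept, N, L, W4, N:W4, L:W4), the distinct rows are:

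- H, W0: 1 0 0 0 0 0
- N, W0: 1 1 0 0 0 0
- L, W0: 1 0 1 0 0 0
- L, W4: 1 0 1 1 0 1

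The W4 and L:W4 columns are identical, and N:W4 is all zeros. Three of the 6 parameters (W4, L:W4, N:W4) are not individually estimable. Only the sum W4 + L:W4 is, and it equals mean(L4) − mean(L0). If software drops L:W4, the coefficient printed as W4 would nominally be the change in healthy skin but is numerically the lesional change.

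With lesional as reference, both interaction columns are all zeros. Two of the 6 parameters are then not estimable, and W4 is the lesional change, correctly labelled. The rank is 4 in either case.

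**Skin, Weeks 0, 2, 4 and 6** (if the stored strips are analysed). There are 3 × 4 = 12 columns, 3 + 1 + 1 + 1 = 6 observed cells, and rank 6. All 2 × 3 = 6 interaction terms are non-estimable.

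**Serum, Weeks 0 and 4.** There are 1 + 1 + 1 + 1 = 4 columns, 3 observed cells, and rank 3. With control as reference, W4 and S:W4 coincide (2 of 4 parameters not individually estimable). With SD as reference, only the interaction is lost (1 of 4).

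**Contrasts.** Not estimable, because each needs an unobserved mean:

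- (L4 − L0) − (H4 − H0)
- (L4 − L0) − (N4 − N0)
- (S4 − S0) − (C4 − C0)

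Estimable:

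- L0 − H0, N0 − H0, L0 − N0
- L4 − L0, L4 − H0, L4 − N0
- S0 − C0, S4 − S0

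**After restatement.** A factor with one level per observed cell has 4 parameters for 4 cells in skin (rank 4) and 3 parameters for 3 cells in serum (rank 3). Every estimable contrast above is a simple difference of its levels.

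**The case against.** The strongest defence is that the text names only an interaction, without main effects or coding. Read as a cell-means model, it has one mean per tissue-time combination. The unobserved combinations are all-zero columns, the observed means are all estimable, and the model can be fitted. That stands, and it is in effect the model recommended here. But the plan does not say so, lists neither cells nor contrasts, and offers a wording that is usually entered as main effects plus interaction. On any reading, the difference-in-change terms remain out of reach.

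The second defence is that the plan never asks for those terms. The sentence introducing the skin model sets two targets, SD against healthy at baseline and change within SD on treatment, and both are estimable. This also stands, and it limits the point. A reader might infer that the exploratory aims cannot be met or that a promised control-adjusted effect is lost. The documents do not support that: the healthy comparison is confined to baseline profiles, and the study is declared open-label.

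A reader might also infer that the fitted numbers would be wrong, or that terms would vanish unnoticed. Neither follows. The surviving Week 4 estimate with healthy as reference equals the lesional change exactly. Software may stop or report the non-estimable coefficients, and which term is dropped follows from the coding, not from chance. What is left is a problem of labelling and specification.

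**Conclusion.** The point holds as a mis-specification of the two exploratory models. Each names an interaction that the design's own sampling cannot supply. The shortfall is 2 in rank for skin at Weeks 0 and 4 (6 columns, rank 4) and 1 for serum (4 columns, rank 3), and no interaction term is estimable under any reference level. The count of individually non-estimable parameters does depend on coding: 3 or 2 of 6 for skin, and 2 or 1 of 4 for serum.

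The consequence is limited. All Week 0 contrasts and the within-patient change in SD are intact. The primary endpoint uses a separate binomial test and is not touched. It would go too far to say that the models cannot be fitted at all, or that the molecular aims fail.

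The rank figures assume main effects plus interaction, and sampling exactly as in Table 1. The serum result takes the group-by-time model as applying to serum, as its paragraph states. Its empty cell therefore comes from the single control blood draw, not from skin sampling.

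**What to change.** Amend Analysis of Mechanistic (Exploratory) Endpoints as follows.

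1. **Skin.** Replace the interaction with a four-level factor: healthy W0, non-lesional W0, lesional W0, lesional W4. Keep the subject random effect. If the Week 2 and Week 6 strips are later analysed, add lesional W2 and lesional W6, giving six levels.
2. **Serum.** Replace the interaction with a three-level factor: control W0, SD W0, SD W4. Keep the subject random effect. The skin factor cannot be reused, because blood has no lesional or non-lesional level.
3. **Contrasts.** For skin: lesional W0 versus healthy; lesional versus non-lesional at W0; lesional W4 versus lesional W0; lesional W4 versus healthy W0. For serum: SD W0 versus control; SD W4 versus SD W0.
4. **Interpretation.** State that the Week 0 to 4 change is an uncontrolled within-patient change, not a control-adjusted treatment effect.

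This costs a few sentences and uses the same samples and software. If the sponsor does want the interactions, non-lesional SD skin, control skin and control blood would have to be sampled again at Week 4, which means an added visit for the 20 controls. Even then, the control comparison would set treated patients against untreated healthy people, not against untreated SD.
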